Study Protocol

Official Title: Delayed sleep phase and risk for adolescent substance use

ClinicalTrials.gov ID (NCT number): NCT03806296

Protocol Date: 08.04.2025

Scientific Background

The acceleration of substance use (SU) that often begins in adolescence can culminate in substance use disorders (SUDs) and a host of other poor outcomes. Mounting evidence indicates that sleep and circadian rhythm disturbances are key contributors to adolescent SU. Delayed sleep phase (DSP), a phenotype characterized by later sleep timing, appears to confer particular risk for elevated SU, and ultimately, SUDs. However, the exact nature of this link and the mechanisms underlying it remain unclear. The extant literature is limited both conceptually (e.g., insufficient attention to neurobehavioral mechanisms) and methodologically (e.g., cross-sectional designs and self-report measures). Circadian misalignment resulting from a mismatch between late sleep timing and early school start times is a compelling potential contributor to elevated SU in adolescent DSP with plausible neurobehavioral mechanisms. We hypothesize that DSP-associated circadian misalignment decreases impulse control and increases reward sensitivity, thereby increasing SUD risk.

NOTE: in the ClinicalTrials.gov protocol, the “Delayed Sleep Phase (DSP)” group is referred to as Late Sleep group, and the “normal phase group” is referred to as the Early/Mid Sleep group

Study Objectives

The proposed study will, for the first time, (1) comprehensively characterize the substance use disorder (SUD) risk profile associated with adolescent delayed sleep phase, and (2) probe whether SUD risk is diminished by altering sleep/circadian timing.

Aim 1: Laboratory Study—Compare DSP group to normal phase group on sleep/circadian factors, neurobehavioral markers, and SU. Compared to the normal phase group, the DSP group will exhibit: (H1a) later circadian phase, shorter sleep duration, and greater circadian misalignment; (H1b) greater behavioral and neural evidence of impulsivity and reward sensitivity; and (H1c) greater odds of cannabis and alcohol use.

Aim 2: Experimental Study—Probe the acute effects of a sleep phase-stabilizing manipulation on sleep and circadian rhythms, as well as neurobehavioral markers of SUD risk. Compared to the control group, the manipulation group will exhibit: (H2a) advances in circadian phase, increases in sleep duration, and reductions in circadian misalignment; and (H2b) reductions in behavioral and neural (fMRI) measures of increased impulsivity and reward sensitivity.

Exploratory Longitudinal Aim: Examine the prospective relationships between DSP characteristics and changes in SU via repeated bi-monthly assessments during a high-risk period for SU initiation/escalation.

Study Design & Methods

The proposed study will, for the first time, (1) comprehensively characterize the SUD risk profile associated with adolescent DSP, and (2) probe whether SUD risk is diminished by altering sleep/circadian timing. The study will assess both established markers of SUD risk and putative neurobehavioral mechanisms (impulsivity and reward sensitivity). Specifically, we propose a comprehensive, multi-method approach to examining DSP's role in SUD risk, combining laboratory, experimental, and longitudinal studies.

We will recruit a sample of 150 eleventh and twelfth graders (16-19 y/o), divided between 100 DSP and 50 normal phase teens. We will focus on cannabis and alcohol use given their prevalent use in adolescents and evident links to DSP. This study combines Laboratory, Experimental, and Longitudinal protocols.

The Laboratory protocol (aka T1 or Baseline phase) compares a group of DSP adolescents to a group of normal phase adolescents on behavioral and neuroimaging (fMRI) tasks tapping impulsivity and reward sensitivity, as well as a circadian phase assessment. This protocol lasts 1 week, with a weeknight overnight visit at the end.

In the Experimental protocol (aka T2 or Post-Manipulation phase), we will probe whether stabilizing circadian phase in the DSP group by using sleep scheduling and chronotherapeutic approaches (e.g., bright light)

improves sleep and neurobehavioral function relevant to SUD risk. This protocol last 2 weeks, with a weeknight overnight visit at the end.

Finally, in the Longitudinal protocol we include repeated follow-up assessments (bi-monthly for the first 6 months; every 6 months afterwards) of sleep and SU to explore longitudinal associations during the high-risk transition to young adulthood.

Eligibility Criteria

General inclusion criteria:

- Age 16-19 years
- Currently in 11th or 12th grade and enrolled in a traditional high-school; or cyber school with synchronous classes (not home-schooled)
- Physically and psychiatrically healthy, as determined by instruments described below
- Provision of written informed consent and assent

Additional inclusion criterion for Experimental protocol

- Meets operational definition of delayed sleep phase (DSP; weekend bedtime ≥ 1 AM)

Exclusion criteria:

- Significant or unstable acute or chronic medical conditions. Examples of such conditions include, but are not limited to central nervous system disorders (e.g., head injury, seizure disorder, multiple sclerosis, tumor), cardiovascular or hemodynamically significant cardiac disease, liver disease (e.g., acute or chronic hepatitis, hepatic insufficiency), active peptic ulcer disease, inflammatory bowel disease, renal failure, arthritis, and diabetes and other endocrine disorders. Individuals with well-controlled health conditions that do not affect sleep or well-being (e.g., well-controlled thyroid disorders, asthma, or ulcer) will not be excluded. To evaluate these criteria, potential participants will complete a locally-developed Medical History Questionnaire. We will exclude women who are pregnant based on self-report during the screening process.
- Past or current bipolar disorder or psychotic disorders, which will be evaluated using the Mini-International Neuropsychiatric Interview for Children and Adolescents (MINI KID).
- Past or current substance use disorders other than alcohol use disorder or cannabis use disorder. We will not exclude participants for subsyndromal symptoms in this domain. The MINI-KID will be used for diagnostic assessment of substance use disorders. We will also assess the likely presence of physiological dependence on alcohol or cannabis via the withdrawal subscales from the Customary Drinking and Drug Use Record (CDDR), and participants that indicate that they would not be able to refrain from use during lab visits will be excluded.
- Past month recreational drug use other than cannabis and nicotine. Cannabis and non-daily nicotine/tobacco use will be permitted, given their high degree of co-use with alcohol. Excluding any nicotine use would also limit generalizability: ~38% of 12th graders report past-month tobacco use (YBRS, 2015), and prevalence is higher in those with regular AU (NSDUH, 2015). Therefore, we will exclude daily nicotine users. Excluding daily nicotine users will markedly reduce confounding effects on sleep and reward function, and non-daily users should not suffer from withdrawal while abstaining during laboratory procedures. Self-reported drug use will be assessed using the Time Line Follow Back method. In addition, a Breathalyzer, salivary cotinine and urine drug screen will be administered prior to the start of the circadian phase assessment visits to the Sleep and Behavioral Neuroscience Center (SBNC).
- Current syndromal sleep disorders other than insomnia and delayed sleep phase disorder, including narcolepsy, restless legs syndrome, obstructive sleep apnea, and current night shift work (i.e., any work occurring between the hours of midnight and 6:00 a.m.). We will not exclude for subsyndromal symptoms or disorders in these domains. We will not exclude for insomnia and delayed sleep phase disorder because of their conceptual overlap and high co-occurrence with delayed sleep phase. Sleep disorders will be diagnosed

according to criteria in the DSM-5 and the International Classification of Sleep Disorders, 3rd Edition, 2014. These disorders will be evaluated using clinical interview and the Structured Interview for Sleep Disorders.

- Medications that interfere with sleep and/or reward function. (e.g., hypnotics, benzodiazepines, anxiolytics, antipsychotics, decongestants and sedating antihistamines, beta blockers, corticosteroids). In order to evaluate medications, participants will complete a listing of current medications, including prescription and over the counter medications, “natural” preparations, and nutritional supplements. Participants must be free of psychotropic medications for a minimum of 2 weeks. We will not exclude participants who are taking antidepressants. We will also not exclude participants who are taking stimulants prescribed for ADHD. However, such participants must be willing and able to discontinue stimulants for 24 hours prior to study visits.
- Conditions that would interfere with the MRI procedures. These include the presence of implanted medical devices such as cardiac pacemaker, aneurysm clip, ear implant, IUD, shrapnel, neurostimulators or other metal devices (e.g. dental braces); and fear of closed spaces.

Statistical Considerations

We will calculate actigraphy and EMA summary measures, examine SU distributions, and perform preliminary analyses. For *a priori* hypotheses, all models will be adjusted for potential confounding factors (e.g., sex). P-values and effect sizes with 95% confidence intervals will be used to evaluate statistical and clinical significance, respectively. After model-fitting, diagnostics will be used to evaluate model assumptions and fit. Transformations or non-parametric methods will be used if normality assumptions are violated. Analyses for the experimental study will adhere to an intent-to-treat principle and include all randomized subjects as assigned.

Aim1:

The DSP group will exhibit (H1a) later circadian phase, shorter sleep duration, and greater circadian misalignment and (H1b) greater behavioral and neural evidence of impulsivity and reward sensitivity: We will use a regression model to test the effect of group on each *a priori* outcome, controlling for relevant confounders. H1c: The DSP group will exhibit greater odds of cannabis and alcohol use. We will use a generalized linear model to test whether the relative risk of cannabis use and/or alcohol use in the past month differs by group, controlling for relevant confounders.

Aim 2:

The manipulation group will exhibit (H2a) advances in circadian phase, increases in sleep duration, and reductions in circadian misalignment; and (H2b) reductions in behavioral and neural (fMRI) measures of increased impulsivity and reward sensitivity. Mixed effect models will be used to test the effect of group on changes in each *a priori* outcome, controlling for relevant confounders.

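### Does the missing model for the Exploratory Longitudinal Aim, with exposure timing and handling of arm unstated, require a change to the plan?

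*Combined protocol and SAP*

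**What the plan says.** Study Design & Methods describes three parts: "This study combines Laboratory, Experimental, and Longitudinal protocols". The third serves the exploratory aim in Study Objectives: "Examine the prospective relationships between DSP characteristics and changes in SU via repeated bi-monthly assessments during a high-risk period for SU initiation/escalation". Its follow-up assessments are "bi-monthly for the first 6 months; every 6 months afterwards) of sleep and SU to explore longitudinal associations", so sleep is measured again alongside substance use.

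Statistical Considerations has model text under two headings only.

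- **Aim 1.** Substance use appears once, under H1c: a "generalized linear model to test whether the relative risk of cannabis use and/or alcohol use in the past month differs by group". This compares past-month use between groups. It does not model change over follow-up.
- **Aim 2.** "Mixed effect models will be used to test the effect of group on changes in each" outcome named in H2a and H2b. Those are circadian, sleep, impulsivity and reward measures. Substance use is not among them.

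Two general sentences come before these. One says that "all models will be adjusted for potential confounding factors (e.g., sex"), but only for a priori hypotheses. The other reads "Analyses for the experimental study will adhere to an intent-to-treat principle and include all randomized subjects as assigned", and so covers the experimental part only.

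**The concern.** The trial itself tries to change the exposure that the longitudinal aim studies. The manipulation is meant to move sleep timing in the delayed-phase group, and sleep is then measured again. The exposure could therefore be a trait recorded at entry or a later value partly set by randomisation, and these answer different questions.

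Arm plays a different part in each. With an entry value, a delayed-phase v normal-phase comparison that ignores arm mixes teens who had the manipulation with teens who did not. If the manipulation lastingly changes use, the comparison shifts: towards the null if use falls, away from it if use rises. With a re-measured value, the manipulation's effect on sleep is already in the exposure, and adjusting for arm discards the randomised part of its variation. If the choice is made after the data are seen, a reader cannot tell which question was planned.

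**Working it through.** **1. What the text covers.** Neither the two model paragraphs nor the two general sentences reach the longitudinal aim. The omission is a fact, and the plan states no wrong rule. There is no planned figure to reproduce: the documents give no use rate, standard deviation, allocation ratio or power for this aim.

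**2. What harm would need.** With an entry-value exposure, three things must hold: randomised teens enter follow-up, follow-up comes after the manipulation, and the manipulation lastingly changes substance use. The design section implies the first two without stating them. Nothing supports the third. The experimental protocol lasts 2 weeks, and Aim 2 is to "Probe the acute effects of a sleep phase-stabilizing manipulation on sleep and circadian rhythms, as well as neurobehavioral markers of SUD risk".

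**3. Rough scale if arm is ignored (entry-value exposure).** From the documents: 100 delayed-phase and 50 normal-phase teens. Assumed: all 100 randomised 1:1, use rates pN (normal) and pD (delayed), and f, the share of the excess pD − pN lastingly removed in the manipulation arm.

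- Shift in the risk difference = −(f/2)(pD − pN).
- Pooled SE at f = 0 is √[pN(1−pN)/50 + pD(1−pD)/100]. For 30% v 50% this is √(0.0042 + 0.0025) = 0.0819, a 95% half-width of 1.96 × 0.0819 = 16 points.
- Coverage is that of the nominal 95% interval for the unshifted difference.

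| pN v pD | SE at f = 0 | Shift at f = 0.5 | Coverage at f = 0.5 | Coverage at f = 1 |
|---|---|---|---|---|
| 30% v 50% | 0.0819 | 5 points | 0.906 | 0.766 |
| 20% v 40% | 0.0748 | 5 points | 0.896 | 0.721 |
| 20% v 30% | 0.0728 | 2.5 points | 0.936 | 0.892 |
| 30% v 40% | 0.0812 | 2.5 points | 0.939 | 0.905 |

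Up to |f| = 0.5 the shift is at most about 0.7 SE. The poor coverage at f = 1 needs the manipulation to remove the whole excess for good.

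This is a two-group comparison at one time point. The aim concerns changes in use over repeated visits, and possibly continuous sleep measures, so the table gives a sense of scale only.

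**4. What the alternative costs.** Comparing control-arm delayed-phase teens (50) with normal-phase teens (50) removes the shift. For 30% v 50% its SE is √(0.0042 + 0.0050) = 0.0959, and 0.0959/0.0819 = 1.17. Over the four rate pairs the ratio runs from 1.17 to 1.20. With no carry-over, power at 30% v 50% falls from 69% to 55%.

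Mean squared error at f = 0.5, 30% v 50%:

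- Pooled: 0.05² + (0.0042 + 0.45 × 0.55/100) = 0.0025 + 0.006675 = 0.009175.
- Control arm only: 0.0092.

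The two are about equal. If use falls, the control-arm contrast is better only above f = 0.50 (20-point excess) or f = 0.96 (20% v 30%), and at no f up to 1 for 30% v 40%. If use rises, the crossover lies between |f| = 0.48 and 0.97.

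**5. Re-measured exposure.** Assumed: within-group and within-arm SD 1 h, arms differing by d hours at follow-up, no direct effect of arm on use, all 150 teens in the model with group adjusted. The exposure sum of squares is 100(1 + d²/4) + 50 = 150 + 25d² without arm and 150 with it, so adjusting for arm multiplies the SE by √(1 + d²/6). For d = 0.25, 0.5, 1 and 1.5 this is a widening of 0.5%, 2%, 8% and 17%. In delayed-phase teens alone the factor is √(1 + d²/4), or 1%, 3%, 12% and 25%.

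**The case for a change.** The best argument for a change is that the gap is specific to this design and cheap to close. The experiment acts on the exposure, no other sentence covers it, and a short addition would fix the exposure time point and the role of arm before anyone sees the data. If the manipulation did have a large lasting effect, an analysis blind to arm would mislead.

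The description of the gap stands in full. So does its consequence for reading: this plan alone cannot show which longitudinal analysis was intended, so any published one should be taken as hypothesis-generating. The plan already says as much by labelling the aim exploratory and attaching no hypothesis to it.

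The case for requiring a change does not stand. No declared hypothesis rests on this analysis, and the second study objective is addressed through H2b. Nor is there one correct choice to impose, since entry-value and re-measured analyses are both legitimate and each way of handling arm has a price. An analyst who fits a delayed-phase indicator together with a manipulation indicator already obtains control-arm delayed-phase v normal-phase as the delayed-phase coefficient. Averaging the two arms instead has the same expected value as pooling at 1:1 and nearly the same SE (0.0815 v 0.0817 at f = 0.5, 30% v 50%), so it would not cure the shift.

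**Conclusion.** The omission is real, but it is missing detail in an exploratory aim, of a kind that analysts ordinarily settle by stating the exposure and showing results with and without arm. H1a to H1c, H2a and H2b are unaffected, and no change to the plan is needed.

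Under the assumed rates, with up to half the excess in use lastingly removed or added, ignoring arm costs at most 5 points, or about 0.7 SE. The contrast that avoids this has an SE 17% to 20% larger. For a re-measured exposure, adjusting for arm costs 0.5% to 17% in SE over the whole cohort.

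These sizes rest on assumed use rates, carry-over, allocation and sleep SD, none of which the documents give, and those for an entry-value exposure come from a single-time-point comparison. The conclusion depends on less: the aim is exploratory, it has no hypothesis, and a lasting effect on substance use is not shown. It would need another look if the longitudinal result were put forward as confirmatory.

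### Does the lack of a primary outcome, multiplicity control or rule for multi-part hypotheses inflate the false-claim rate for H2b?

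*Combined protocol and SAP*

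**What the plan says.** The opening paragraph of Statistical Considerations states: "P-values and effect sizes with 95% confidence intervals will be used to evaluate statistical and clinical significance, respectively". The tests are then described hypothesis by hypothesis:

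- **H1a and H1b:** "We will use a regression model to test the effect of group on each" of the outcomes fixed in advance.
- **H1c:** a generalized linear model, to "test whether the relative risk of cannabis use and/or alcohol use in the past month differs by group".
- **H2a and H2b:** "Mixed effect models will be used to test the effect of group on changes in each" of the prespecified outcomes.

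H2b itself predicts "reductions in behavioral and neural (fMRI) measures of increased impulsivity and reward sensitivity". The measures are not listed. Study Design & Methods speaks, for the Laboratory protocol, of "behavioral and neuroimaging (fMRI) tasks tapping impulsivity and reward sensitivity", and names no task, contrast or brain region.

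The documents do not rank the outcomes, state an alpha, give a multiplicity adjustment, or say whether a multi-part hypothesis stands on one part or on all. Only the longitudinal aim is labelled exploratory.

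**The concern.** Aims 1 and 2 are set out as directional hypotheses tested by p-value, and several have more than one part. H2b and H1b each pair two modalities (behavioral, neural) with two constructs (impulsivity, reward sensitivity). One measure per pairing would give four tests, and more are possible. The wording of H1c does not settle whether cannabis and alcohol use form one outcome or two.

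With no stated rule, one favourable result out of four or more could be presented as support for the whole hypothesis. The choice between any part, all parts and a claim per outcome could also be made after the results are known. At stake is the error rate attached to the main experimental claim, that the sleep manipulation reduces markers of substance-use risk.

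**Working it through.** The documents state no alpha, power or family-wise error rate, so there is no figure of theirs to reproduce. The check compares the error under the rules that the text leaves open.

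**Inputs**
- Alpha: not stated. Two-sided 0.05 is inferred from the 95% intervals, so a null outcome gives a false claim in the hypothesised direction with probability 0.025.
- Number of H2b outcomes, k: not stated. Four is an assumption (2 modalities × 2 constructs, one measure each). Composites would give fewer and several tasks per pairing would give more.
- Correlation r between test statistics: assumed equal for all pairs, at 0, 0.5 and 0.8.
- All null hypotheses are taken as true for the error rates.

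**Rule 1: any one reduction supports H2b**
- Independent: 1 − 0.975^4 = 1 − 0.9037 = 9.6%.
- Correlated: 1 − ∫ φ(u) · Φ((1.96 − √r·u)/√(1 − r))^4 du = 7.8% at r = 0.5 and 5.7% at r = 0.8.
- A t-test simulation (assumed 50 per arm, 100,000 runs) gave 9.6% at r = 0 and 5.8% at r = 0.8.
- If a hit in either direction counted: 1 − 0.95^4 = 18.5% when independent, 11.4% at r = 0.8, against 5% for one test.
- With eight outcomes, hypothesised direction only: 18.3% / 12.5% / 7.9% at r = 0 / 0.5 / 0.8.

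**Rule 2: one claim per outcome**
- Each claim has a 2.5% error in the hypothesised direction, whatever k or r. The chance that at least one of the four claims is wrong is still the Rule 1 figure, but each claim is then about one outcome and is read beside the other three.

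**Rule 3: all parts needed for H2b**
- The error cannot exceed that of any single test, so it is at most 2.5%. With all four null it is 0.025^4, effectively zero, if independent, and about 0.5% at r = 0.8.
- The price is power. At an assumed 80% for each outcome, joint power is 0.8^4 = 41% if independent, 56% at r = 0.5 and 66% at r = 0.8.

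**Cost of the obvious remedy, Holm within each hypothesis (k = 4)**
- Strictest step: 0.05/4 = 0.0125. An effect with 80% power at 0.05 has about 61% there (two-sample t-test, assumed 50 v 50).
- If all four effects are real with 80% power each, simulated power per outcome is 73% / 71% / 70% at r = 0 / 0.5 / 0.8.
- With four null outcomes the chance of a false claim falls to 2.5% / 2.2% / 1.6%.
- Five hypotheses (H1a, H1b, H1c, H2a, H2b) would remain five separate families. If all nulls are true and the families are taken as independent, the study-wide chance in the hypothesised direction is up to 1 − 0.975^5 = 11.9%.

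**The case for a change.** The strongest argument for a change is that the omission is real and the text is not cut off at this point. The plan itself presents Aims 1 and 2 as a priori hypotheses judged by p-value, so calling the work mechanistic does not remove the question. Even at a correlation of 0.8, the any-part rate of 5.7% is more than twice 2.5%. Settling the outcomes and the claim rule before outcome analysis would need only wording.

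Part of this stands. From these documents a reader cannot confirm which outcomes were fixed in advance, or how many there are. That is missing detail.

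The step to an inflated error rate does not stand. It needs a decision rule that appears nowhere in the plan. The hypotheses join their parts with *and*, and the models are applied to outcomes one at a time, so both natural readings (Rules 2 and 3) avoid attaching a 9.6% error to a claim for H2b. The count of four is also an inference from the wording.

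Nor is the concrete remedy a free gain. Holm costs roughly 7 to 19 points of power (80% to between 73% and 61%), leaves the choice of family arguable and still names no primary outcome. The plan also commits to effect sizes with 95% intervals, so readers will not have p-values alone to go on.

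**Conclusion.** No change to the plan follows. Following it as written means testing and reporting each prespecified outcome, with its effect size and interval, and speaking for a whole hypothesis only when its parts agree. That keeps the error at 2.5% per claim, or at most 2.5% for the whole hypothesis, in the hypothesised direction at an inferred two-sided 0.05.

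The 9.6% / 7.8% / 5.7% figures are correct arithmetic for a rule that the plan does not adopt. They rest on four assumed outcomes, all effects null and assumed correlations of 0, 0.5 and 0.8. The unlisted outcomes and unstated claim rule are details that analysts can settle sensibly within the text. Formal adjustment within each hypothesis is a trade of power for error control on which statisticians can fairly differ in a mechanistic study of this kind.

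### Does the normality fallback let the group comparisons lose their covariates, or leave too much choice of method?

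*Combined protocol and SAP*

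**What the plan says.** Everything relevant is in Statistical Considerations. For the a priori hypotheses, the general paragraph states that "all models will be adjusted for potential confounding factors (e.g., sex"). It continues: "P-values and effect sizes with 95% confidence intervals will be used to evaluate statistical and clinical significance, respectively". Next comes the check, "After model-fitting, diagnostics will be used to evaluate model assumptions and fit", and then the fallback: "Transformations or non-parametric methods will be used if normality assumptions are violated".

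For H1a and H1b the Aim 1 text adds "We will use a regression model to test the effect of group on each" prespecified outcome, with control for confounders. H1c is a separate case: "We will use a generalized linear model to test whether the relative risk of cannabis use and/or alcohol use in the past month differs". A normality check therefore has no bearing on it. Aim 2 uses mixed effect models, again with control for confounders. The fallback sentence is general and therefore covers the continuous outcomes of both aims.

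The design is set out in Study Design & Methods: "We will recruit a sample of 150 eleventh and twelfth graders (16-19 y/o), divided between 100 DSP and 50 normal phase teens". The Laboratory protocol "compares a group of DSP adolescents to a group of normal phase adolescents", so the Aim 1 groups are defined by sleep phenotype and not by randomization.

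**The concern.** The usual two-group rank test takes no covariates and yields a p-value without a regression-type effect estimate. If that test were the fallback, two of the plan's own requirements, adjustment and an effect size with its interval, would lapse just where the data are awkward. This would matter most in Aim 1, where the covariates are the only control for confounding.

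There is also a question of discretion. The plan does not say what counts as a violation of normality, or when to transform and when to go non-parametric. Residual checks come after fitting, when the group coefficient can already be seen. Two analysts could reach different verdicts on one outcome, or one analyst could try several methods and keep the most favourable.

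**Working it through.** **Reading the sentences together.** The adjustment rule covers all models for the a priori hypotheses, and the reporting rule asks for an effect size with interval without exception. Neither is confined to models with normal errors, and both stand shortly before the fallback in the same paragraph. An unadjusted rank test would break both. Adjusted regression on a log or rank scale keeps the covariates and gives a coefficient with an interval.

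**Inputs.** From the documents: group sizes 100 and 50, sex as the named covariate, and the 95% level. The plan states no power, alpha, SD or effect, so there is no figure of its own to reproduce. Assumed: two-sided 5% level, log-normal outcomes, and the sex shares and sex effects given below. With 4,000 replicates the Monte Carlo standard error near 5% is √(0.05 × 0.95 / 4,000) = 0.0034, about 0.3 percentage points.

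**1. Covariates kept or dropped.** Type I error with log-SD 0.8, no true group effect, 4,000 replicates:

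| Sex share in the two groups | Sex effect (log-scale SD) | Adjusted log | Adjusted rank | Unadjusted Mann-Whitney |
|---|---|---|---|---|
| 50% v 50% | 0.5 | 4.8% | 4.8% | 5.0% |
| 60% v 40% | 0.3 | 6.0% | 5.8% | 6.7% |
| 60% v 40% | 0.5 | 5.3% | 5.3% | 8.9% |
| 60% v 40% | 0.8 | 4.9% | 5.0% | 14.3% |

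The harm is confined to the last column, which is the analysis that the adjustment rule excludes. With 10,000 replicates and log-SD 1, the adjusted rank analysis gave 4.7-5.5% and the adjusted log analysis 4.7-5.4%.

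**2. The procedure as written.** Fit the adjusted raw-scale model and test its residuals (Shapiro-Wilk as an example). If normality is rejected, use the adjusted rank analysis, or take logs first and ranks only if the log residuals also fail. Over log-SD 0.15 to 1, type I error was 4.4-5.5%, essentially nominal.

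**3. The worst use of the remaining freedom.** Always taking the smaller of the adjusted log and adjusted rank p-values gave 5.6-6.5% (log-SD 1, 10,000 replicates) and 5.3-7.0% (log-SD 0.8, 4,000 replicates). This is an upper bound, because the plan's trigger is the residual check and not the group p-value.

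**4. Disagreement between methods.** With a true effect of 0.5 log units and log-SD 1, adjusted raw and adjusted rank analyses disagree on p < 0.05 in about 27% of simulated studies. That pair is not an open choice. At log-SD 1 the Shapiro-Wilk test rejected the raw residuals in 100% of studies, and the sentence then moves the analyst off the raw scale. The choice that does remain, log against rank, disagreed in about 5%.

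**5. Realism of the skew.** Log-SD 1 puts 95% of values between exp(-1.96) = 1/7.1 and exp(1.96) = 7.1 times the median. For sleep duration with an assumed median of 7 h, that runs from about 1 h to about 50 h. At milder skew, with the effect held at 0.5 SD on the log scale, raw and rank disagree in 7.0% of studies at log-SD 0.3 and 4.5% at log-SD 0.15.

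**The case for a change.** The best argument for a change is that a two-group rank test is arguably not a model, so a literal reader could think the adjustment rule does not reach it. If sex were both unequal between the groups and prognostic, that reading would cost real error control, as the last column of the table shows. Even with covariates kept, neither the criterion nor the route is fixed, and a sentence or two would settle both at almost no cost.

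Part of this stands. The documents do not name the fallback method, its effect measure or the criterion, and a line saying that any fallback keeps the covariates and reports an interval would do no harm. But the literal reading has to set aside both the adjustment rule and the reporting rule, as well as the control for confounders repeated under each aim. Checking residuals after fitting is ordinary practice, since residuals exist only then. A sentence that still named no method would also leave the choice to be made later.

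**Conclusion.** No change is needed. The fallback sentence is brief, and the rules around it fill the gap: an analyst who follows the whole paragraph uses an adjusted analysis with an interval. On that reading type I error is 4.4-5.5%, and the most opportunistic choice between the two adjusted fallbacks brings it to about 5-7%. The gap reaches the continuous outcomes of Aims 1 and 2 and matters most for Aim 1, which is not randomized.

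These sizes rest on assumed log-normal outcomes, assumed sex shares and effects, and a two-sided 5% level, because the documents supply none of these. That the covariates and the interval carry over to the fallback follows from the plan's text and does not depend on the simulations.
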